8.2.2 Individual Preparatory Session 3 and Safety Review

At Preparatory Session 3 and Safety Review, the site team will confirm the participant continues to be eligible for the study by reassessing specified safety criteria and ensuring that the participant continues to agree to all lifestyle modifications. This may require approval from the Medical Monitor for the initial participants until confidence is established. If any eligibility requirements are not met before or during Preparatory Session 3 and Safety Review, the participant will be considered a Pre-Dosing Early Termination.

For eligible participants at Preparatory Session 3 and Safety Review, the therapy team or other qualified site staff will:

- Complete the third 90-minute Preparatory Session with the purpose of confirming all enrollment is met and completing final preparation for the first Experimental Session.
- Inquire about any possible changes in health to ensure the participant continues to meet all eligibility requirements. Record AEs as described in [Section 8.7: Adverse Events, Serious Adverse Events, and Other Safety Reporting](#).
- Inquire about concomitant medication use and adherence.
- Administer Since Last Visit C-SSRS to determine suicidal risk.
- Perform urine pregnancy test (for PAPB only).
- Perform urine drug test.
- Actively support participant in the completion of Baseline self-reported measures. Completion of measures does not need to be recorded.

8.2.3 Independent Rater Baseline Assessment

At Baseline, an IR will measure the baseline CAPS-5 (referred to as Baseline CAPS-5 T1) via tele-assessment. This visit may be recorded to video to establish inter-rater reliability. The IR will also administer the SDS and DSP-I at this time. The Baseline CAPS-5 score (T1) will be used for baseline comparison for statistical analyses but will not be used for eligibility determination.

8.2.4 Support Person

During the Screening and Preparatory Period, the participant will identify an appropriate support person to stay with the participant on the evening of the Experimental Session. Participants will be required to be escorted to and from the study site after Experimental Sessions. The support person is not required to be the same as the escort for the participant. There may be more than one support person(s), and they will be responsible for providing companionship as needed overnight and contacting the study team with any questions or concerns. Any support person spending the night with the participant will be required to meet a member of the therapy team in person, during the Preparatory Period or in advance of the appropriate Experimental Session in-person to be oriented to the role. An escort who is responsible only for transportation need not meet with the therapy team to perform that role. The participant will provide contact information for the appropriate support person(s) in advance of each Experimental Session.

8.2.4.1 Orienting the Support Person

The support person(s) will receive printed instructions, including contact information of the study physician, therapists, investigator, and Study Coordinator and what to do in the case of an emergency. The support person will not provide therapy to the participant. Minimal discussion is acceptable, but only if initiated by the participant. The support person should not interpret the participant's experience or act as therapist. The therapy pair will discuss this explicitly with the support person and include this information in the written instructions.

The main roles of the support person include:

- Ensuring the participant is safely transported to and from the study site as appropriate (may be completed by a separate support person or escort).

- Ensuring that the participant does not leave the overnight location without accompaniment and does not leave the participant alone at the overnight location. The participant may have privacy at the overnight site.
- Ensuring the participant has a comfortable place to sleep and discuss the plan for wakeup, breakfast, and travel time for the next day's Integrative Session.
- Seeing to the participant's needs for food and liquids, including providing dinner and breakfast in accordance with the participant's dietary preferences.
- Eating with the participant unless they ask to be left alone.
- Cleaning up after the participant, including doing the dishes and handling bedding.
- Keeping all participant information confidential.
- Supervising the participant to ensure they do not consume drugs or alcohol on the night of the Experimental Session and that phone/computer time is limited.
- Remaining sober throughout the entire overnight stay.
- Remaining available to participant's needs throughout the night, but may sleep if the participant is sleeping.

8.3 Treatment Period

During the Treatment Period, which occurs over a duration of 7-9 weeks (Experimental Session 1 to Integrative Session 2.4), participants will complete two treatments. Each treatment consists of an Experimental Session, followed the morning after by an Integrative Session, phone follow-ups every other day for 14 days, a second Integrative Session within 2 weeks, a third Integrative Session within 3 weeks, and a fourth Integrative Session within 4 weeks. The Experimental Sessions will be scheduled 3 to 5 weeks apart.

8.3.1 Experimental Sessions

There will be two open-label Experimental Sessions (Experimental Session 1 and 2). Procedures for MDMA-assisted therapy will remain the same across all sessions and all procedures regardless of dose received. Experimental Sessions must be at least 6 hours long, measured from 30 minutes prior to IMP administration. At both Experimental Sessions, a dose of 100 mg MDMA (equivalent to 120 mg MDMA HCl) will be administered followed by a supplemental dose of 34 mg or 50 mg MDMA (equivalent to 40 mg or 60 mg MDMA HCl) 1.5 to 2 hours after the initial dose, unless tolerability issues emerge with the first dose or the participant declines. Strength of supplemental dose will be the same for all participants and will be determined by drug supply availability at the start of the trial.

Table 6: Experimental Sessions

Visit	Individual or Group	Visit Timing
Experimental Session 1	Individual	1 to 14 days after Preparatory Session 4; up to 28 days after Baseline CAPS
Experimental Session 2	Group	~4 weeks (21 to 35 days) after Experimental Session 1

8.3.1.1 Pre-IMP administration

- On the day of the Experimental Session, the participants will arrive approximately 30 to 60 minutes prior to IMP administration.

- The site team will ensure the participant has not used caffeine or nicotine 2 hours prior and fasted for 10 hours prior to IMP administration and agrees to comply with all other requirements per [Section 5.3 Lifestyle Considerations](#).
- The site team will inquire about any possible changes in health to ensure the participant continues to meet all eligibility requirements and record AEs, as described in [Section 8.7.5 Method of Detecting AEs and SAEs](#).
- The site team will complete symptom-directed physical exam, urine drug screen, pregnancy test (for PABP only), and concomitant medication review.
 - A positive drug screen will be reviewed by the site physician and may be cause for delaying IMP administration to a later time, rescheduling the session to a later date, or withdrawing the participant from the study, based on Medical Monitor review.
 - A positive pregnancy screen is cause for withdrawal from the protocol.
- The therapy team will administer Since Last Visit C-SSRS.
- The therapy team will review procedures for the Experimental Session with the participant and discuss the participant's goals, intentions, and concerns and some of the commonly experienced effects of MDMA.
- During the Group Experimental Session, all four co-facilitators will be present.
- Baseline blood pressure, body temperature, and pulse will be measured just prior to administration of the initial dose.
- A symptom-directed physical examination, or additional vital signs measurements, may be conducted at any time if clinically indicated.

8.3.1.2 During the Experimental Session

- After video recording has begun, a qualified staff member will administer the initial dose of IMP with water. The participant will sit or recline on comfortable furnishings. Eyeshades and a program of music will be provided for the participant if they wish to use them. Whenever they wish, participants may speak to the therapy team, who will provide guidance and support, as needed.
- During the Individual Experimental Session, after the first hour, if the participant has not spoken spontaneously, the therapy team will check in with them about the nature of the experience. For the rest of the experience, as appropriate, the therapy team will support and encourage the participant in emotional processing and resolution of whatever psychological material is emerging, as described in the Treatment Manual.
- During the Group Experimental Session, participants will primarily be engaged in their own internal experience, interacting with their assigned facilitator(s) as needed; group processing will be reserved for before MDMA ingestion and toward the end of the session.
- Fluids will be provided throughout the session but not to exceed three liters overall.
- Blood pressure, body temperature, and pulse will be measured approximately 1.5 to 2 hours after the initial dose, before the supplemental dose is administered.
- The site physician (if not part of the therapy team) will provide escalation criteria individualized to the participant to determine if the team site physician should be contacted.
 - If escalation criteria are met, a member of the therapy team will contact the site physician with a brief description of how the session is progressing and the recent vital signs to determine if the supplemental dose should be withheld.
 - If medical attention is needed, the site physician will provide further instruction or consult the Medical Monitor.

- A supplemental dose will be administered with a glass of water approximately 1.5 to 2 hours after the initial dose, unless the participant experiences tolerability issues.
- Food will be provided during the latter part of the session.

8.3.2 Telephone Contact After Experimental Sessions

A member of the therapy team will follow-up with the participant by telephone every other day for 14 days after each Experimental Session. Calls will not be made if there is an Integration Session scheduled the same day.

The goal of the telephone contact is to assess health changes, ensure participant safety, and offer support. Each call will last on average 5 to 15 minutes but could be longer to address participant concerns and to adequately assess wellbeing. Additional telephone contact can be initiated at the request of the therapy team or participant.

At each telephone contact, the therapy team will:

- Inquire about any possible changes in health, assess the participant's mental health and the status of any previously recorded AEs, and record AEs as described in [Section 8.7: Adverse Events, Serious Adverse Events, and Other Safety Reporting](#).
- Inquire about concomitant medication use and compliance.
- Offer support in accordance with the Treatment Manual.
- Administer the Since Last Visit C-SSRS.

8.3.3 Integrative Sessions

After each Experimental Session, four Integrative Sessions will take place. Each session will consist of 90 minutes of therapy.

On the morning after the Experimental Session, the participants will be escorted to the study site via car, rideshare, or public transportation, as participants are not allowed to drive within 24 hours of administration of MDMA.

In addition to completing the study procedures, the therapy team will discuss and review events that occurred with the participant during the Experimental Session, including thoughts, feelings, and memories. If necessary, the therapy team will help the participants to reduce any residual psychological distress they are experiencing. The therapy teams will also encourage the transfer of states of acceptance, feelings of intimacy, closeness, and reduced fear experienced in Experimental Sessions to emotionally threatening everyday situations. The therapy teams will be supportive, validate the experience, and facilitate understanding and emotional clearing.

Table 7: Integration Sessions after Experimental Sessions

Following First Experimental Session		
Visit	Individual or Group	Visit Timing
Integration Session 1.1	Individual	Morning after Experimental Session 1
Integration Session 1.2	Group	~1 week (3-14 days) after Experimental Session 1
Integration Session 1.3	Group	~2 weeks (10-21 days) after Experimental Session 1
Integration Session 1.3	Group	~3 weeks (17-28 days) after Experimental Session 1; 1-7 days before Experimental Session 2
Following Second Experimental Session		
Integration Session 2.1	Group	Morning after Experimental Session 2
Integration Session 2.2	Group	~1 week (3-14 days) after Experimental Session 2
Integration Session 2.3	Group	~2 weeks (10-21 days) after Experimental Session 2
Integration Session 2.4	Group	~3 weeks (17-28 days) after Experimental Session 2

8.4 Follow-up Period and Study Termination

During the Follow-up Period and Study Termination, participants will complete a final CAPS-5 assessment and attend a Study Termination visit.

Table 8: Primary Outcome and Study Termination

Visit	Individual or Group	Visit Timing
Primary Outcome	Individual	after Experimental Session 2
Study Termination	Individual	after Outcome

8.4.1 Follow-up Period

After the final Integrative Session 2.4, participants will enter follow-up for approximately 4 weeks (+/-2 weeks) with no protocol required visits until the final Outcome assessment followed by a Study Termination. Participants will have access to therapy teams for support if needed, and additional visits via telephone, tele-assessment, or in person can be scheduled if requested. Participants will continue to comply with protocol requirements for concomitant medications until after Study Termination.

8.4.2 Independent Rater Final Assessment

Participants will have a final Outcome assessment at the completion of the follow-up period. An IR will conduct the assessments via tele-assessment. These assessments may be recorded to establish inter-rater reliability. The results may be shared with site staff during supervision by the therapy training team. Participants who have withdrawn from treatment will also complete a final

Outcome assessment immediately upon withdrawal. The IR will also administer the SDS and DSP-I.

8.4.3 Study Termination

Study Termination will take place 1 week (0-9 days) after the final CAPS-5 assessment and can occur on the same day as Outcome visit. Participants who have withdrawn from treatment but have continued for follow-up will also complete this assessment immediately upon withdrawal.

After all Study Termination measures and assessments are completed, the participant is considered terminated from the study. The participant can resume normal everyday life. The study team will provide a plan moving forward, which may include a referral for additional medical or therapeutic care, as described in [Section 8.4.4 Plan Moving Forward](#). Eligible participants may be invited to participate in a future long-term follow-up (LTFU) extension study, which will be conducted under a separate protocol.

8.4.4 Plan for Moving Forward

At Study Termination, participants will be provided with a plan for moving forward. This plan will summarize treatments completed, current medications, and contact information for more information about the study if needed. Participants may request a referral for further therapeutic or medical care if appropriate. Enrolled participants who terminate the study early will be provided a plan for moving forward at their last contact. Screen Failures will be provided a referral if requested.

8.5 Eligibility and Efficacy Assessments

8.5.1 Primary Outcome Measure and Reliability

8.5.1.1 Clinician-Administered PTSD Scale for DSM-5 (CAPS-5)

The CAPS-5 is a semi-structured interview that assesses index history of DSM-5-defined traumatic event exposure [114], including the most distressing event, time since exposure, to produce a diagnostic score (presence vs. absence) and a PTSD Total Severity score [114]. The CAPS-5 rates intrusion symptoms (intrusive thoughts or memories), avoidance, cognitive and mood symptoms, arousal and reactivity symptoms, duration and degree of distress and dissociation. The total severity score is a sum of symptom frequency and intensity scores for the subscales B (re-experiencing), C (avoidance) and D (hypervigilance) and ranges from 0 to 136, with higher scores indicating greater severity of PTSD symptoms. The CAPS-5 takes approximately 90 minutes to complete.

Assessment and Reliability of CAPS-5

The CAPS-5 will be administered by a blinded IR via tele-assessment. Interviews will be conducted by the centralized remote IR pool to enhance quality control by reducing site-level variation in interview fidelity and quality. The IRs will be trained and supervised by a research reliable trainer and will be supervised by qualified personnel. Interviews may be recorded in as many instances as necessary to establish reliability of a random selection of interviews for accuracy.

Per the CAPS-5 Training Manual for the IR Pool, IRs will ensure that every single item-level score is collected in every CAPS-5 interview. The CAPS-5 is administered by the IR in a neutral, non-leading manner to minimize the chance for bias. Avoiding a biased administration can be achieved by adhering to administration guidelines verbatim and only deviating from the script to clarify, re-direct, or query further if behavioral examples are needed to determine the appropriate symptom intensity rating. Avoiding building therapeutic/clinical rapport beyond the basic level of rapport needed to conduct the interview in the research setting also minimizes the chance for bias. Remote assessment assures that the rater who is collecting the Primary Outcome will not witness Experimental Sessions and the acute effects of IMP. Interviews may be recorded in as many instances as necessary to establish reliability of a random selection of interviews for accuracy. After the initial screening visit, the IRs will be blinded to visit number, number of treatments received, and any study data for the participant. IR visits will be assigned based on availability.

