2.2 Background

2.2.1 Posttraumatic Stress Disorder (PTSD)

PTSD is a serious debilitating disorder associated with increased mortality and cardiometabolic morbidity. PTSD is a stress-related psychiatric condition that may occur following a traumatic event such as war, disaster, sexual abuse, violence, terrorism, and accidents. The four main symptom categories described in the Diagnostic and Statistical Manual of Mental Disorders, 5th edition (DSM-5), include arousal and reactivity, avoidance of triggers, negative thoughts and feelings, and intrusive thoughts and nightmares. PTSD negatively impacts a person's daily life, resulting in fractured relationships, inability to maintain employment, diminished cognitive and psychosocial functioning, substance abuse, high-cost healthcare utilization, and increased depression and suicide risk. People who suffer from PTSD often relive the experience through nightmares and flashbacks, have poor sleep quality, and feel detached or estranged. Confronting overwhelming internal distress and frightening external environments can also lead to high levels of depersonalization and derealization, which led clinicians to identify a dissociative subtype of PTSD in the DSM-5. Adaptations in normal brain function have been observed in imaging studies of patients with PTSD that underlie alterations in emotional processing and regulation, cognition, and many aspects of behavior, though clinical symptoms and changes in brain activity are not homogenous across patients [1]. The dissociative subtype occurs in 12 to 30% of people with PTSD and is characterized by detachment and emotional numbing and visualized in the brain as overmodulation of affect mediated by midline prefrontal inhibition of limbic regions, while the non-dissociative subtype presents symptoms of hyperarousal and re-experiencing, an emotional under modulation mediated by the failure of prefrontal inhibition of the same limbic regions [2, 3]. Patients suffering from the dissociative subtype of PTSD typically have early childhood trauma and appear to be particularly difficult to treat, with mixed response to existing evidence-based treatments. PTSD affects United States military veterans many times more than the general population [4] and is estimated to cost the VA billions of dollars per year, including suicides, medical comorbidities, and lost productivity [5]. The link between interpersonal problems and PTSD symptoms among United States military veterans has been well-established in the literature [6, 7].

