MAPS initiated an international series of Phase 2 clinical trials to develop the medical use of MDMA-assisted therapy for patients with chronic, at least moderate PTSD (CAPS-4 score: 50+), with at least 6 months of symptoms. Intent-to-treat (ITT) analysis of primary efficacy and safety data from six MAPS-sponsored MDMA PTSD Phase 2 clinical trials worldwide (MP1, MP2, MP4, MP8, MP9, MP12) consisting of 107 blinded participants with chronic PTSD was completed in 2016 [110]. In these studies, PTSD, independent of cause, appears treatable with a two- to three-session treatment package of MDMA-assisted therapy, as assessed by difference in CAPS-4 severity scores from baseline to 1 to 2 months after the final experimental session. Large placebo-subtracted effect sizes (Cohen's $d=0.9$), initial indications of efficacy, and favorable safety outcomes led to the approval of MDMA for the treatment of PTSD as a Breakthrough Therapy Designation (BTD) by the FDA in 2017 for expedited drug development [111]. Improvements were durable at least 12 months after the last Experimental Session in 91 participants who received a therapeutically active dose of MDMA in these Phase 2 studies with 67% not meeting PTSD diagnostic criteria per CAPS-4 assessment [112].

MAPS completed a pivotal Phase 3 clinical trial (MAPP1) in 2020, further demonstrating the efficacy and safety of MDMA-assisted therapy for treatment of PTSD [113]. In this randomized, double-blind, placebo-controlled study, 90 participants with severe PTSD (CAPS-5 score: 35+ with at least 6 months of symptoms) were treated across 15 sites. Similar to Phase 2 results, PTSD symptoms were significantly attenuated by MDMA-assisted therapy. Manualized therapy in conjunction with MDMA (divided-doses of 80+40 mg or 120+60 mg MDMA HCl) was statistically superior for PTSD treatment in CAPS-5 severity scores from Baseline to 2 months after three blinded experimental sessions in comparison to therapy paired with an inactive placebo ($p<0.0001$). At the primary endpoint, 67% of participants in the MDMA group no longer met diagnostic criteria for PTSD, compared to 32% of the placebo group. Based on the successful completion of MAPP1, a confirmatory Phase 3 clinical trial (MAPP2) is currently underway encompassing a sample of participants with moderate to severe PTSD.

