9.3.2 Primary Endpoint Analysis

The primary endpoint is the change in mean CAPS-5 Total Severity Scores from Baseline to Primary Outcome Visit. Analysis of the primary endpoint will be conducted using a ANCOVA model with change from baseline score as the outcome and baseline CAPS-5 score as an independent variable. Adjustment for additional potential covariates will be explored. Additional details will be provided in the SAP.

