9.3.4 Exploratory Endpoints Analyses

An exploratory responder analysis will characterize clinical significance of PTSD treatment effect from Baseline to Primary Outcome Visit based on the following categories:

- **Treatment Response:** 10-point or greater reduction in CAPS-5 Total Severity Score.
- **Loss of Diagnosis:** 10-point or greater reduction in CAPS-5 Total Severity Score and no longer meeting PTSD diagnostic criteria on CAPS-5.
- **Remission:** CAPS-5 Total Severity Score of under threshold or less and no longer meeting PTSD diagnostic criteria on CAPS-5.

Exploratory sub-group analyses may be conducted when possible to evaluate effectiveness by treatment group and individual demographic characteristics (e.g., age, gender, ethnicity, index trauma, dissociative subtype of PTSD, presence of secondary traumatic stressors during the assessment period with LEC-5, diagnosis of comorbid depression, diagnosis of comorbid psychiatric diagnosis, group cohort, and number of Experimental Sessions completed). Exploratory analyses of secondary outcome measures will be described in the Statistical Analysis Plan.

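### The protocol's only scoring rule for the CAPS-5 total, the primary endpoint, covers three subscales although the protocol says the instrument rates four symptom domains, and its 0 to 136 range is doubtful

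*Protocol*

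**What the plan says.** Section 9.3.2 of the protocol makes the CAPS-5 total the primary measure: "The primary endpoint is the change in mean CAPS-5 Total Severity Scores from Baseline to Primary Outcome Visit". Section 9.3.4 uses the same total for three exploratory responder categories. Treatment Response and Loss of Diagnosis both require a "10-point or greater reduction in CAPS-5 Total Severity Score". Remission uses a cut-off on the total, for which the text gives no number.

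The total is defined in one place, section 8.5.1.1. That paragraph first describes the content of the interview: "The CAPS-5 rates intrusion symptoms (intrusive thoughts or memories), avoidance, cognitive and mood symptoms, arousal and reactivity symptoms". It then gives the total as the "sum of symptom frequency and intensity scores for the subscales B (re-experiencing), C (avoidance) and D (hypervigilance) and ranges from 0 to 136".

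Section 2.2.1 describes the disorder in the same four-part way. Its DSM-5 categories "include arousal and reactivity, avoidance of triggers, negative thoughts and feelings, and intrusive thoughts and nightmares".

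**The concern.** Two adjoining statements about the primary measure disagree. The interview is said to cover four symptom domains, but the total adds up three subscales, and none of the three is labelled as cognition and mood. The stated range raises a separate doubt, because it does not match a 20-item DSM-5 symptom scale under either usual way of scoring an item.

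The study has no formal hypothesis test (9.1), so the size of the CAPS-5 change is itself the efficacy result. If the total is computed by the written rule, a symptom domain is missing from it. If it is computed another way, the reported endpoint is not the one the protocol defines. In both cases a reader cannot tell what a change of a given number of points means, or whether it can be set beside the sponsor's other CAPS-5 results.

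**Working it through.** **1. Domains rated against subscales summed**

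| Rated by the interview (8.5.1.1) | DSM-5 category (2.2.1) | Subscale in the total (8.5.1.1) |
|---|---|---|
| Intrusion | Intrusive thoughts and nightmares | B, re-experiencing |
| Avoidance | Avoidance of triggers | C, avoidance |
| Cognition and mood | Negative thoughts and feelings | none |
| Arousal and reactivity | Arousal and reactivity | D, hypervigilance (nearest label) |

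Three of the four domains have a subscale in the total. This step needs no outside source.

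**2. Can the stated range be reproduced?**

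Maximum = number of items x maximum points per item. The protocol gives neither figure for the CAPS-5, so 136 cannot be rebuilt from its own inputs. Two assumptions are needed:

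- Points per item: 4 for a single 0-4 rating, or 8 for frequency 0-4 plus intensity 0-4.
- Number of items: the only count of DSM-5 symptom items in the protocol is the PCL-5's 20 (8.5.3.5). It is assumed here to carry over to the CAPS-5. The alternative of 17 comes from 136 / 8 = 17.

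| Items | Points per item | Maximum |
|---|---|---|
| 20 | 4 | 80 |
| 20 | 8 | 160 |
| 17 | 4 | 68 |
| 17 | 8 | 136 |

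Only 17 x 8 gives 136. With 20 items, 136 would need 136 / 20 = 6.8 points per item, which is not a whole number.

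**3. What the 10-point threshold means on each candidate range**

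- 10 / 136 = 7.4%
- 10 / 80 = 12.5%
- 10 / 160 = 6.3%

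As an illustration, if 10 points had been set on a 0-80 scale, the same share of a 0-136 scale would be 136 x 10 / 80 = 17 points. The protocol does not say on which range the threshold was set.

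**4. Power and sample size**

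Section 9.5 says the sample size is not based on power, and 9.1 plans no test. Nothing there needs to be recalculated.

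**The case against.** The strongest reply is that no one need score from this sentence. Section 8.5.1.1 has the independent raters work to a separate CAPS-5 training manual and record every item in every interview. The item data should therefore exist, a correct total can be computed from them, and section 9.0 leaves technical detail to an SAP finalised before database lock. On this view the flaw is a slip in an instrument description.

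Part of that stands. Nothing in the protocol shows that any score will actually be computed wrongly, and item-level collection means the error can be repaired without loss of data. But the text on the training manual concerns how interviews are conducted and items collected, not which items are summed. The protocol has not left the scoring open: it states a rule. An SAP that scored the instrument otherwise would contradict that rule.

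The objection also correctly limits three stronger readings that a reader might infer:

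- *That this is definitely the older CAPS scoring.* The product 17 x 8 = 136 suggests it, but the protocol gives neither the item count nor the scoring of the CAPS-4.
- *That the protocol's severity cut-offs prove the range wrong.* Section 2.2.6 describes "at least moderate PTSD (CAPS-4 score: 50" or more in earlier trials and "90 participants with severe PTSD (CAPS-5 score: 35+ with at least 6 months of symptoms" in the Phase 3 trial. These are two named instruments. Calling it impossible for severe to start at 35 when at least moderate starts at 50 requires both to run from 0 to 136, and no CAPS-4 range is stated.
- *That the 10-point threshold is wrong for the scale.* Section 9.3.4 ties it to no range, and a 0-80 range is an assumption. The documents support only that the threshold cannot be interpreted yet.

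**Conclusion.** The point holds as a contradiction within the protocol about its primary measure. By its labels, the total covers three of the four symptom domains that the protocol says the CAPS-5 rates, and it omits cognition and mood. That part rests on the text alone and is firm.

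The doubt about the range is weaker. It depends on the CAPS-5 having 20 items, borrowed from the PCL-5, scored at 4 or 8 points each. On that assumption the maximum is 80 or 160, and 136 fits neither.

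The two parts should not be added together. If the sentence is taken literally, a domain is missing from the total. If it was carried over from another version of the scale, its grouping and range describe a different total, and the loss is not simply one whole cluster. The protocol does not settle which applies, and the sentence needs correcting under either reading.

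The consequences are confined to the definition of the primary endpoint, the meaning of any reported change in points, and the exploratory responder categories.

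**What to change.** 1. Replace the scoring sentence in 8.5.1.1 with the clusters, item count, per-item scale and range of the Total Severity Score, taken from the scoring manual of the CAPS-5 instrument that the protocol cites. The replacement should cover all four symptom domains and agree with 2.2.1. The wording has to come from that manual, since the protocol does not contain the details.
2. Confirm that the eCRF and the independent rater pool's scoring use the same definition.
3. Confirm in 9.3.4 that the 10-point threshold and the remission cut-off refer to that range.

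The cost is one amended sentence in the protocol and a short check of the scoring in the eCRF and the rater pool. It is best done before the SAP is finalised, so that both documents define the same score. No change to design, sample size or visit schedule is needed.
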